7.2.6 Final Study Contact (6 months + 2 weeks)

The final study contact will take place by mail. If the patient has not become pregnant, the patient will be mailed the follow up Ferti-QOL questionnaire to fill out with a self addressed prepaid return envelope. Any pregnancies that occur up to 6 months after randomization will be followed to completion and will not receive a FertiQol questionnaire.

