1.0 Objectives

1.1 Study Objectives

The primary objective is to collect the ongoing pregnancy rate among subjects in the study. The co-primary objective is observe the safety and tolerability of Lipiodol UF®. Secondary objectives will be to document the relative pain during the Sono HSG procedure and any changes in quality of life as a result of the procedure according to the contrast agent. Exploratory outcomes will be the feasibility of blinding the patient and observer to the type of contrast medium injected at the end of the Sono HSG procedure and the prevalence of Anti-Chlamydial antibodies and association with outcomes. The results from this pilot trial will guide the design of a larger multi-center clinical trial examining Lipiodol UF® as a contrast agent during Sono HSG.

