2.3 Study Rationale

The rationale for this trial is to further explore the use of oil based contrast media, specifically Lipiodol UF® both in the context of a contrast agent and as a potential treatment agent for women from couples with infertility. We specifically propose, eventually, to both build on and replicate the H2Oilie trial conducted in the Netherlands. We will build on the H2Oilie trial by utilizing ultrasound instead of fluoroscopy to conduct our HSG. Ultrasound based hysterosalpingography, i.e. Sono HSG, can be conducted in an outpatient setting by a single physician. It avoids patient and physician exposure to radiation, in many cases the additional trip to an inpatient hospital, the requirement of staffing by both radiologic and gynecologic personnel, and the greater expense of fluoroscopic HSG. We will expand the patient population from primarily women with unexplained infertility, to all women with infertility who will receive expectant management or conventional first line therapies. We will exclude women who will be going on to in vitro fertilization (IVF) as the chosen infertility therapy, because IVF as a first line

therapy is only applicable to women with tubal occlusion/tubal disease or couples with severe oligospermia requiring oocyte insemination or intracytoplasmic sperm injection (ICSI).

Our specific hypothesis is that tubal patency testing by Sono HSG with an oil-based contrast medium, Lipiodol UF®, will lead to higher ongoing pregnancy rates compared to the use of normal saline as a contrast medium with equal safety as a saline contrast agent.

The intervention will involve injection of 10 cc of Lipiodol UF® versus saline at the time of Sono HSG as a control. Lipiodol UF® is approved as an injection agent for HSG by the U.S. FDA.

The underlying rational for the pilot trial is to obtain preliminary data and to pilot the methodology to conduct a larger multi-center trial definitively powered to document the safety and efficacy of Lipiodol UF® as a primary contrast agent during Sono HSG.

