7.2 Study Procedures

	Screening	Enrollment/Study Visit Time = 0	Post Procedure = 2 – 4 weeks	Final Study Contact Time = 6 mos (+2 weeks)	Pregnancy Follow up Up to 15 mos
Inclusion/Exclusion Criteria	X				
Review Informed Consent and Obtain Per Telephone	X				
Schedule Sono HSG	X				
Collect Written Informed Consent		X			
Randomize		X			
Perform Urine Pregnancy Test		X			
Perform Sono HSG with Saline and then Study Agent		X			
Administer FertiQol Questionnaire		X		X	
Assess Patient VAS score		X			
Assess echogenicity of study media		X			
Assess adequacy of blinding by patient and physician		X			
Obtain Blood for Anti-Chlamydial Antibodies		X			

	Screening	Enrollment/Study Visit Time = 0	Post Procedure = 2 – 4 weeks	Final Study Contact Time = 6 mos (+2 weeks)	Pregnancy Follow up Up to 15 mos
Obtain blood for TSH and Free T4		X	X		
Collect adverse events since test				X	
Obtain Release of Pregnancy Records as necessary					X
Collect all pregnancy outcomes					X

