7.2.5 Follow Up (up to 15 months)

Follow up will take place via review of medical records. Patients will follow American Society of Reproductive Medicine (ASRM) guidelines for treatment.(13) Currently, based on Level I evidence that would be clomiphene/IUI for unexplained infertility (14) and letrozole with timed intercourse for polycystic ovary syndrome.(15) The initial consent will allow access to all medical records in the Electronic Health Record including any resulting pregnancy. Data collected will include any potential adverse events as well as information on the participant's course of infertility treatment/any resulting pregnancy outcomes up to 15 months after the procedure. If a patient seeks infertility or pregnancy care outside the institution we will obtain a release of records form from the patient at their last visit to our infertility clinic to obtain release of these records at the end of the 6 month participation in the study (or longer if a patient conceives at the end of the 6 month window of study participation). We will not follow any conceptions that occur more than 6 months after performing the Sono SHG. A conception is defined as a positive urine or serum pregnancy test for hCG. All conceptions will be followed up to the completion of that pregnancy.

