8.3 Statistical methods

The analysis dataset will follow a modified intention to treat (mITT) where all evaluable subjects will be analyzed. For the pilot study, an evaluable subject is a subject that has been randomized and has completed the Sono HSG.

Descriptive statistics for continuous data will be reported as the mean (standard deviation) or as the median (25th percentile, 75th percentile) if the distribution is not normally distributed. Descriptive statistics for categorical will be reported as a frequency and percentage. All hypothesis tests will be two-sided and tested at a significance level of 0.05. All analyses will be conducted using SAS software, version 9.4 (SAS Institute Inc., Cary, NC) or R software, version 3.3.3 (R Foundation for Statistical Computing, Vienna, Austria).

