8.3.2. Secondary Endpoint Analysis

A two-sample t-test will be used to compare the Lipiodol UF® to saline groups with respect to continuous outcomes, such as VAS scores, change in Ferti-QOL scores from baseline to 6 mos after Sono HSG, and anti-chlamydial antibody levels. The effect size from the two-sample t-tests will be quantified using the difference in means and 95% confidence interval. In the event the data do not meet parametric assumptions, the data will either be transformed (e.g., a logarithmic transformation) in order to satisfy parametric assumptions or a non-parametric Wilcoxon rank-sum test will be used to compare the treatment groups.

A Pearson's chi-square test, or Fisher's exact test if the expected cell counts are <5, will be used to compare the live birth proportions, as well as detectability (yes/no) for anti-chlamydial antibodies, between the Lipiodol UF® and saline groups. A relative risk and 95% confidence interval used to quantify the effect size.

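### The 6-month FertiQoL is withheld from women who conceive, so the planned between-arm test of FertiQoL change does not compare the randomised groups

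*Combined protocol and SAP*

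**What the plan says.** All references are to the combined protocol and SAP.

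- **Objective (1.1).** A secondary objective is to document "any changes in quality of life as a result of the procedure according to the contrast agent".
- **Data collection (7.2.6).** The follow-up form is conditional on pregnancy status: "If the patient has not become pregnant, the patient will be mailed the follow up Ferti-QOL questionnaire". The section then adds: "Any pregnancies that occur up to 6 months after randomization will be followed to completion and will not receive a FertiQol questionnaire".
- **Definition (7.2.5).** "A conception is defined as a positive urine or serum pregnancy test for hCG".
- **Analysis (8.3.2).** A two-sample t-test, with transformation or a Wilcoxon rank-sum test as fallback, compares the arms on continuous outcomes that include "change in Ferti-QOL scores from baseline to 6 mos after Sono HSG".
- **Analysis set (8.3).** The set is "modified intention to treat (mITT) where all evaluable subjects will be analyzed". A woman is evaluable once she has been randomised and has completed the Sono HSG.
- **Schedule (7.2).** The row "Administer FertiQol Questionnaire" is marked at the study visit and at 6 months, with no pregnancy condition.
- **Hypothesis (2.3).** Lipiodol "will lead to higher ongoing pregnancy rates compared to the use of normal saline as a contrast medium".

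No section defines a separate population for the FertiQoL analysis or says how the withheld scores are to be handled.

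**The concern.** Sections 7.2.6 and 8.3/8.3.2 cannot both be carried out as written. The analysis section promises a randomised comparison in all evaluable women. The data-collection rule leaves 6-month scores only for those who did not conceive.

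The restriction is not ordinary non-response. Conception happens after randomisation and is closely tied to the primary endpoint: every woman who reaches an ongoing pregnancy loses her 6-month score. Read with the hCG definition in 7.2.5, so do women with an early loss or an ectopic pregnancy. Because the trial hypothesises more ongoing pregnancies with Lipiodol, it also predicts that more scores will be removed from that arm.

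Three things follow:

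- A difference between arms could reflect who is left rather than what the agent did.
- Any quality-of-life effect that acts through conceiving is excluded by construction.
- A sizeable share of the scores is never collected and cannot be recovered once the 6-month window has closed.

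**Working it through.** **Plan's own figures.** The documents give no SD, power or precision target for FertiQoL. The base used here is the 25 evaluable women per arm in section 8.2. Inflating for the stated 10% loss gives 50/(1 − 0.10) = 55.6, rounded up to 56, which matches section 8.1.

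**Inputs.**
- 25 evaluable women per arm (8.2).
- Ongoing-pregnancy rates at 6 months of 39.2% (Lipiodol) and 28.5% (water-based agent), from the earlier trial in 2.2. The protocol does not adopt these as planning values, so they serve only as an illustration.
- Two-sided 0.05 level (8.3).
- Assumption: 85% or 75% of conceptions become ongoing pregnancies. The documents give no figure.
- Assumption: every mailed form is returned.

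**Step 1: scores available.** Women with a possible 6-month score = 25 × (1 − rate).
- Lipiodol: 25 × 0.608 = 15.2. Saline: 25 × 0.715 = 17.9.
- Missing by design: (0.392 + 0.285)/2 = 33.9%, or 16.9 of 50.

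Conceptions exceed ongoing pregnancies, so the rates are also divided by 0.85 and by 0.75.

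**Step 2: precision.** The 95% CI half-width for a difference in means, in SD units, is t(0.975, n1 + n2 − 2) × √(1/n1 + 1/n2).

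| Scenario | Conception rates | Women with a score | Missing | Half-width (SD) |
|---|---|---|---|---|
| Form sent to all | not applicable | 25 / 25 | 0% | 0.569 |
| Rates from 2.2 | 39.2% / 28.5% | 15.2 / 17.9 | 33.9% | 0.712 |
| Rates ÷ 0.85 | 46.1% / 33.5% | 13.5 / 16.6 | 39.8% | 0.751 |
| Rates ÷ 0.75 | 52.3% / 38.0% | 11.9 / 15.5 | 45.1% | 0.792 |

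**Step 3: selection bias.** Suppose the agent has no effect on FertiQoL change, and that a latent normal propensity to conceive has correlation ρ with that change. Among women who do not conceive, the mean change is −ρ × φ(c)/(1 − p), where p is the conception rate and c is the standard normal quantile at 1 − p. The Lipiodol minus saline difference is then:
- rates from 2.2: −0.157 × ρ
- rates ÷ 0.85: −0.189 × ρ
- rates ÷ 0.75: −0.220 × ρ

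For ρ of 0.3 to 0.5 (assumption) this gives −0.047 to −0.079 SD at the rates in 2.2, and −0.057 to −0.110 SD across the two higher-rate scenarios. Relative to the half-width at the rates in 2.2: 0.047/0.712 = 7% and 0.079/0.712 = 11%. A negative ρ of the same size reverses the sign. The bias is zero if ρ is zero or if the agent does not affect conception.

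**Step 4: effect left out.** If conceiving shifts FertiQoL change by 0.25 to 1.0 SD (assumption), the part of the between-arm effect that runs through conception is (0.392 − 0.285) × shift = 0.107 × 0.25 to 0.107 × 1.0, or 0.03 to 0.11 SD. The planned test cannot see it.

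**The case against.** The strongest reply is that FertiQoL is an instrument for people with infertility, so sending it only to women who are still not pregnant may be a deliberate and sensible choice. If the target is change in those women, no scores are lost by design, and the only fault is that 8.3.2 does not name the target. This stands in part. The documents neither give that reason nor show whether the tool suits pregnant women. If the reason is accepted, it supports the rule in 7.2.6 but does not rescue the between-arm test, because the subset is still formed after randomisation.

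Other points against:

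- **Weight.** This is a pilot. Quality of life is absent from the endpoint list in 1.3 and from the pilot goals in 8.2. That limits the seriousness, but 1.1 names it as a secondary objective and 8.3.2 gives it a test. Section 1.1 also says that the results will guide a larger trial, so the rule could be carried forward.
- **Definition.** Section 7.2.6 speaks of pregnancy and does not cite the hCG definition in 7.2.5. Excluding early losses and ectopics is the likelier reading but is not explicit, and the 40% to 45% missing figures depend on it.
- **Illustration.** The rates come from a fluoroscopic trial with a water-based comparator, mainly in unexplained infertility. Here the population is broader, both arms first receive saline, and women go on to first-line treatment. The sizes are indicative only.
- **Schedule.** An unfootnoted mark in a summary grid is weak evidence of conflict. The real mismatch is between 7.2.6 and 8.3/8.3.2.

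**Conclusion.** The concern holds. As written, the FertiQoL test is conditioned on a post-randomisation event that the trial expects the agent to influence. It therefore cannot answer the quality-of-life objective, and it contradicts the stated analysis set.

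The main costs are the lost randomised interpretation and, if all women are the target, the loss of about a third of the scores. The bias is small beside the sampling error in a trial of this size, and its sign rests on an assumed positive correlation. The half-widths assume full return of the forms, so real precision would be worse in every scenario.

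Describing change in women who did not conceive remains legitimate. The point should be fixed, but it is confined to this one secondary objective.

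**What to change.** Choose one of two options before 6-month forms fall due.

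1. **Keep the comparison.** Amend 7.2.6 so that the 6-month FertiQoL goes to every evaluable woman whatever her pregnancy status, which also matches the schedule in 7.2. In 8.3.2, compare the arms in all of them, adjusting for baseline FertiQoL. The adjustment improves precision but does not cure selection; collecting the form from everyone does that. Cost: about 17 more mailed forms at the rates in 2.2, or 20 to 23 at the assumed conception rates. At the $10 card in section 14.0 that is roughly $170 to $230. Downside: some items may fit pregnant women less well, and section 11.0 already lists questionnaire discomfort as a risk, which matters for women with a recent loss.

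2. **Keep the collection rule.** If the sponsor judges the tool unsuitable in pregnancy, leave 7.2.6 as it is and remove the FertiQoL test from 8.3.2. Report change descriptively by arm, labelled as applying to women with no conception by 6 months. Give the number excluded for conception in each arm, and make no causal statement by contrast agent. Add a matching note to the schedule and to the analysis set in 8.3. Cost: wording only, but the between-arm test is given up.

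Under the second option, 7.2.6 should also say whether a positive hCG test alone is enough to withhold the form.

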7.3 Duration of Participation

Study duration will typically be 6 months(+2weeks), but can be up to 15 months if conception occurs at the end of study period.

7.4 Test Article(s) (Study Drug(s) and/or Study Device(s))

7.4.1 Description

Lipiodol UF® is an FDA- approved oil-based radiopaque contrast agent indicated for: hysterosalpingography in adults, lymphography in adult and pediatric patients selective hepatic intra-arterial use for imaging tumors in adults with known hepatocellular carcinoma (HCC).

7.4.2 Treatment Regimen

The physician will dose at 2 cc increments into the uterine cavity via the Sono HSG Catheter, visualizing the endometrial cavity via ultrasound and ruling out filling defects as well as visualizing the left and the right fallopian tube to document patency. Up to 10 cc can be instilled into the uterine cavity.

7.4.3 Method for Assigning Subject to Treatment Groups

The randomization scheme for this study will use 1:1 group allocation via variable-size, random permuted blocks to ensure that the number of participants in each treatment arm is balanced after each set of B randomized participants, where B is the block size. The study coordinator will use the randomization module in the password protected, secure REDCap database software to randomize the participant. Participants will be entered consecutively. The Penn State Investigational Pharmacy will have access to the randomization scheme and perform the preparation of study contrast to maintain double blinding.

7.4.4 Subject Compliance Monitoring

The drug will be administered to the subject under the supervision of the physician performing the procedure.

7.4.5 Blinding of the Test Article

The drug will be prepared and blinded by Investigational Drug Services at Penn State Hershey. They drug will be dispensed in an opaque syringe and opaque tubing will be used during the procedure to maintain the double blind.

7.4.6 Receiving, Storage, Dispensing and Return

7.4.6.1 Receipt of Test Article

The study agent, Lipiodol UF®, will be purchased from Guerbert LLC, Princeton, NJ and shipped to the Investigational Pharmacy at Penn State Hershey which will store and dispense the product for the study. The study agent will be ordered in 10cc vials. The Investigational Pharmacy at Penn State Hershey will also prepare the normal saline control for Sono HSG.

7.4.6.2 Storage

The study agent Lipiodol UF® will be stored at room temperature 15°-30°C (59°-86°F) and protected from light in the investigational pharmacy until prepared for use.

7.4.6.3 Preparation and Dispensing

The study agent Lipiodol UF® or the control normal saline will be re-packaged prior to administration in a 10 cc opaque glass syringe by the Penn State Investigational Pharmacy and will be coded in a de-identified fashion. It will be dispensed upon physician prescription to study personnel.

7.4.6.4 Return or Destruction of the Test Article

All unused Lipiodol UF® will be returned to Guerbet, LLC at the end of the study.

7.4.6.5 Prior and Concomitant Therapy

Participants who are planning to undergo IVF therapy in the next six months will not be included in the study.

8.0 Subject Numbers and Statistical Plan

8.1 Number of Subjects

Fifty-six subjects will be randomized and receive study intervention, twenty-eight per randomization arm. We estimate that we will need to screen one hundred patients in order to meet this goal.

8.2 Sample size determination

For pilot studies it has been suggested that sample sizes ranging anywhere from 12 to 60 subjects per group would provide sufficient data to obtain estimates of the primary outcome in order to power a future definitive clinical trial, as well as provide sufficient evidence to assess feasibility, blinding safety, and regulatory considerations.(16) A sample size of 50 evaluable subjects (25 per group) should be sufficient in order to satisfy the goals of this pilot study (i.e., feasibility of binding the contrast medium, obtaining estimates for a formal power calculation of a future trial, and evaluating the safety of the contrast medium). We anticipate, however, that 10% of the subjects will either drop-out prior to study completion or be randomized but not be able to have a Sono HSG performed because they change their minds during the procedure and opt out or they have bilateral tubal occlusion or a hydrosalpinx. Also, subjects may not be evaluable as result of technical errors associated with manipulation of the required glass syringe for study drug administration. Therefore, we will recruit a minimum of 60 subjects up to a maximum of 72 subjects, terminating enrollment once we have reached the goal of 50 evaluable subjects.

8.3 Statistical methods

The analysis dataset will follow a modified intention to treat (mITT) where all evaluable subjects will be analyzed. For the pilot study, an evaluable subject is a subject that has been randomized and has completed the Sono HSG.

Descriptive statistics for continuous data will be reported as the mean (standard deviation) or as the median (25th percentile, 75th percentile) if the distribution is not normally distributed. Descriptive statistics for categorical will be reported as a frequency and percentage. All hypothesis tests will be two-sided and tested at a significance level of 0.05. All analyses will be conducted using SAS software, version 9.4 (SAS Institute Inc., Cary, NC) or R software, version 3.3.3 (R Foundation for Statistical Computing, Vienna, Austria).

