3.0 Inclusion and Exclusion Criteria

3.1 Inclusion Criteria

1. Female, age 18-40 years
2. Eligible for Sono HSG for fertility testing
3. In good general health
4. Willing and capable of complying with the study procedures
5. At least one patent tube and no endometrial pathology on Sono HSG
6. Ready to undergo infertility treatment immediately after the test
7. Not planning on IVF therapy in the next 6 mos

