3.2 Exclusion Criteria

1. Known tubal or endometrial (polyp, submucous fibroid, etc.) pathology
2. At high risk for tubal disease due to history of Pelvic Inflammatory Disease
3. Known hypersensitivity to Lipiodol UF® or known allergy to iodine containing contrast media or shellfish
4. Endometrial pathology on Sono HSG requiring further evaluation (as per the performing physician)
5. Bilateral tubal occlusion on Sono HSG
6. Unable to tolerate potential pain associated with the study.
7. Requiring IVF due to severe male factor, known pelvic adhesions, etc.
8. Couples with decreased male factor fertility rate (i.e., low sperm count or motility, i.e. less than 5 million/mL concentration on semen analysis

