7.2.3 Baseline Assessments/Study Intervention

Case report forms documenting the history will be obtained, the Ferti-QOL (12) quality of life survey will be obtained. Serum for Anti-Chlamydial antibodies as well as Free T4 and TSH will be drawn before or after the Sono HSG depending on the patient's reason for visit, as often a baseline progesterone and hCG level are obtained prior to the Sono HSG if the patient is to go on immediately to treatment. The rationale for the Anti-Chlamydial antibodies is that we have shown they are associated with failure to conceive and pregnancy loss including ectopic pregnancies in our prospective randomized controlled trials (9). Samples drawn for anti-chlamydial antibodies will be sent to the study sponsor's laboratory for analysis. Free T4 and TSH will be collected in order to assess thyroid function. A urine pregnancy test will be performed. We will then proceed with the Sono HSG. This begins first with a routine pelvic ultrasound. Then a speculum is inserted into the vagina and then the Sono HSG catheter is inserted through the cervical canal into the uterine cavity and the balloon is inflated to maintain a seal at the cervical canal. A special device, i.e. the FemVue system, will then be used to infuse normal saline while at the same time creating bubbles to ease ultrasound visualization. The speculum is removed and the transvaginal ultrasound probe is inserted. The Sono HSG begins with infusion of normal saline via the FemVue catheter. After a patient has had an SHG with a normal cavity and at least one patent tube as determined by the performing physician, the patient will receive the study contrast or control saline which will be in an opaque glass syringe and connected to the uterine catheter via opaque tubing to allow double blinding of physician and patient. The study agent will be shaken vigorously to induce turbulence and air bubbles to ease tracking of the agent and then infused in 2 cc increments under ultrasound

visualization while the physician again visualizes the uterine cavity and patency of the fallopian tube(s). Infusion will cease with documentation of a normal cavity and tubal patency or when 10 cc have been infused. The amount of contrast infused will be recorded. After infusion the patient will be asked to assess the degree of pain she experienced by the VAS scale and both physician and patient will be asked to document a guess as to what contrast medium was used as study agent.

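### The only analysis set requires a completed Sono HSG, so women who stop during the study agent, or whose study syringe fails, can be excluded after randomisation

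*Combined protocol and SAP*

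**What the plan says.** Randomisation takes place before any study procedure (7.2.2), so every exclusion that arises in the procedure is post-randomisation.

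Section 8.3 names a single modified intention-to-treat set made up of evaluable women, where "an evaluable subject is a subject that has been randomized and has completed the Sono HSG". It defines no all-randomised set and no safety set.

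The procedure has two phases (7.2.3). Saline is infused first in everyone. The study agent follows only "After a patient has had an SHG with a normal cavity and at least one patent tube", in 2 cc steps, and infusion ends when a normal cavity and patency have been documented or when 10 cc is reached. The infused volume is recorded, and VAS pain and the blinding guess are taken after infusion.

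Section 8.2 plans for 50 evaluable women. It allows 10% for women who drop out later or cannot have the Sono HSG, and adds that errors in handling the glass syringe used to give the study drug may also make a woman non-evaluable. Recruitment is 60 to 72 and stops at 50 evaluable.

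**The concern.** A set restricted to completers is safe only if completion is settled before the randomised agent can influence it. Here the text allows completion to depend on what happens during the agent. A woman who stops because of pain or a reaction could leave the analysis, and so could one whose syringe fails partway.

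Safety and tolerability is a co-primary objective (1.1), and VAS discomfort is listed among the primary safety parameters (10.2). Early stops are the women who say most about tolerability, and removing them would tend to make the worse-tolerated agent look better. They would also leave the pregnancy denominator, so that comparison would no longer be fully randomised. The pilot's estimates are meant to design a larger trial, and enrolment stops on the same undefined count.

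**Working it through.** **1. What a completed Sono HSG means.**

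- *Saline examination only.* Eligibility is judged by "At least one patent tube and no endometrial pathology on Sono HSG" (3.1) and "Bilateral tubal occlusion on Sono HSG" (3.2), and 7.2.3 gives the agent after the saline examination. On this reading every woman who starts the agent is evaluable under 8.3.
- *Saline, then agent.* The schedule in 7.2 lists "Perform Sono HSG with Saline and then Study Agent" as one item, and 1.1 refers to "the type of contrast medium injected at the end of the Sono HSG procedure". Section 8.2 also counts women with bilateral occlusion as unable to have the Sono HSG, although 7.2.3 finds occlusion in the saline phase. On the saline-only reading such women could be evaluable without receiving any agent, which contradicts 8.2.

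The second reading fits better. On it, a woman who stops during the agent may be non-evaluable.

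**2. Syringe errors.** This reason appears in 8.2 but not in the 8.3 definition. It has no rate and no statement of whether agent has already entered.

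**3. Later drop-outs.** Section 8.2 counts them within its 10% loss. Section 8.3 keeps them, because they were randomised and had the procedure. The two sections use different definitions of evaluable.

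**4. The plan's own count.** 50 / (1 − 0.10) = 55.6, rounded up to 56, or 28 per arm. This reproduces 8.1. The 60 to 72 in 8.2 does not follow from 10%: 1 − 50/60 = 16.7% and 1 − 50/72 = 30.6%.

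**5. Possible effect on pregnancy (assumed counts).** Take 10/25 against 7/25. RR = 0.40/0.28 = 1.43. SE(log RR) = √(1/10 − 1/25 + 1/7 − 1/25) = 0.404, so the 95% CI is 0.65 to 3.15. Suppose k early stops had been excluded from the first arm. Restoring them with none or all pregnant gives:

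| k | Range of proportions | RR |
|---|---|---|
| 1 | 10/26 to 11/26 | 1.37 to 1.51 |
| 2 | 10/27 to 12/27 | 1.32 to 1.59 |
| 3 | 10/28 to 13/28 | 1.28 to 1.66 |

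**6. Possible effect on VAS (assumed distributions).** Scores are normal with location 40 mm in one arm and 50 mm in the other, scale 20 mm, truncated to 0–100. The actual means are about 41 and 50 mm and the SDs 18.7 and 19.1, so the true difference is 9.00 mm by simulation. The shares at 70 mm or above are 6.7% and 15.4%. If a fraction of those women stop and are excluded:

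| Fraction excluded | Stops per 56 women | Difference left (mm) | Shrinkage (mm) |
|---|---|---|---|
| 10% | 0.6 | 8.79 | 0.2 |
| 25% | 1.5 | 8.45 | 0.55 |
| 50% | 3.1 | 7.83 | 1.2 |

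The 95% half-width with 25 per arm is t(48) × SD × √(2/25) = 2.011 × 20 × 0.283 = 11.4 mm. With the truncated SDs (pooled √[(18.7² + 19.1²)/2] = 18.9) it is 10.7 mm. As a deliberately extreme case, dropping the 3 highest of 28 scores in one arm only lowers that arm's mean by about 0.195 SD, or 0.195 × 20 = 3.9 mm.

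**The case against.** Much is already protected. AEs are collected from consent (10.4), and 10.7 does not restrict the AE test to evaluable women, so AE capture is not the main exposure. VAS is taken after infusion, which need not mean a full infusion. All women are followed (3.3.2), so the pregnancy outcomes of excluded women should be obtainable. Both arms use opaque syringes and tubing with physician and patient blinded, and nothing reports different stopping or syringe-failure rates by arm. The 8.2 opt-outs may simply be women in whom the test was never done. By the figures above, any bias sits well inside sampling error.

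All of this stands, and it limits the size of the problem. It does not settle which women enter the VAS and pregnancy comparisons. Recorded volume cannot settle it afterwards either, because infusion may properly end at any 2 cc step.

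Two stronger inferences are tempting, and the documents support neither.

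- Section 8.1 states "Fifty-six subjects will be randomized and receive study intervention, twenty-eight per randomization arm", and 2.3 says "The intervention will involve injection of 10 cc of Lipiodol UF® versus saline at the time of Sono HSG". Set against 50 evaluable, a reader might infer that six women are expected to be treated and then excluded. But 56 is exactly 50 inflated for 10% loss, so the wording is more likely loose.
- A reader might take 10% off the 60 to 72 recruits and attribute the rest of the excess over 50 to syringe failures. The 10% mixes procedural losses with later drop-outs, whom 8.3 keeps, and 60 to 72 is a recruitment range with a stop at 50. It does not forecast exclusions.

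**Conclusion.** The concern holds in limited form and should be fixed. On the better-supported reading of 8.3, and separately through the syringe sentence in 8.2, the plan permits post-randomisation exclusion at or after the start of the agent. The VAS comparison is the most exposed, and the pregnancy denominator comes next. Sections 8.2 and 8.3 also disagree on later drop-outs.

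The documents do not show that such exclusions will occur, how many there would be, or that they would differ by arm. The size is therefore unknown. With one to three excluded women the RR of 1.43 moves within 1.28 to 1.66, against a CI of 0.65 to 3.15. The VAS difference moves by 0.2 to 1.2 mm, or 3.9 mm in the extreme one-sided case, against a half-width of about 11 mm. The pregnancy counts, pain distributions and stopping fractions are all assumptions. In a 50-woman pilot with no power claim, any bias is probably smaller than sampling error. The case for acting is that the remedy is cheap and the same definition could carry into the larger trial.

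**What to change.** 1. In 8.3, replace the completion criterion with: all randomised women who passed the saline phase, with eligibility recorded before the study syringe is connected, analysed as randomised for pregnancy whether or not the infusion was completed. Saline-phase exclusions are then made before the arms differ and under blinding.
2. Analyse VAS and AEs in all women who received any study agent, and name that set in 8.3.2 and 10.7. It still leaves out women whose syringe failed before any agent entered, so report those by arm.
3. Record VAS, and the reason infusion ended, for every woman who started the agent.
4. Tabulate exclusions and early stops by arm, timing and reason.
5. Reconcile the evaluable counts and loss reasons in 8.1 and 8.2 with this definition, including the syringe errors and the later drop-outs.

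The cost is wording changes, one added CRF item, and slight dilution of the pregnancy effect if women with a failed syringe and no agent are kept. Take the 39.2% and 28.5% in 2.2 (RR 1.38) as assumed rates, with 25 treated Lipiodol women and k untreated women at the control rate. The Lipiodol rate is then (25 × 0.392 + k × 0.285)/(25 + k). For k = 1, 2 and 3 this is 38.8%, 38.4% and 38.1%, and the RR becomes 1.36, 1.35 and 1.34.
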